#### **4.4.3.4 Mean Turesky Plaque Index at Week 6 and Week 12**

For comparison between ‘Toothpaste/Mouthwash and Reference Toothpaste’, the following null and alternative hypotheses will be evaluated:

[figure not shown]
- H0: There is no difference in the Mean Overall TPI at Week 6 and 12 between the Toothpaste/Mouthwash and Reference Toothpaste.
- H1: There is a difference in the Mean Overall TPI at Week 6 and 12 between the Toothpaste/Mouthwash and Reference Toothpaste.
- H0: There is no difference in the Mean Interproximal TPI at Week 6 and 12 between the Toothpaste/Mouthwash and Reference Toothpaste.
- H1: There is a difference in the Mean Interproximal TPI at Week 6 and 12 between Toothpaste/Mouthwash and Reference Toothpaste.

TPI (Overall and Interproximal) will be analyzed as described for primary analysis ([Section 4.4.1.2](#)), using the Baseline Mean Interproximal/Overall TPI value as covariate respectively. The adjusted means and SEs of the two product groups together with the product difference, SE, 95% CI of the difference and p-value will be provided in Table 14.2.8.2.1 (Overall TPI) and in Table 14.2.9.2.1 (Interproximal TPI) for the mITT population. The % adjusted mean difference will also be presented.

#### 4.4.3.5 Exit Satisfaction Survey Questionnaire (Toothpaste/Mouthwash Treatment Arm)

At the end of the study (Visit 4/Week 12), subjects in Toothpaste/Mouthwash treatment arm will be asked to rate their level of satisfaction with the Toothpaste and the Mouthwash using a Numeric Rating Scale (NRS). The NRS is an 11-point ordinal scale used to assess the subject's satisfaction with the Toothpaste and Mouthwash. The scale ranges from 0 (completely dissatisfied) to 10 (completely satisfied), with higher scores indicative of greater satisfaction.

Subjects will be asked to record the numeric value on the segmented scale that best describes their level of satisfaction after 12 weeks twice daily use and indicate why they select a particular score in answer to the question 'Please give more details on why you are satisfied or dissatisfied with the product' (free text response).

A summary of the number and percentage of subjects reporting at each level of the NRS and the cumulative number of subjects reporting at each level or higher at Week 12 will be presented in Table 14.2.10.1.1 and the numeric (integer) NRS score at Week 12 will be summarized

descriptively in Table 14.2.10.1.2 by the test product Toothpaste and the test product Mouthwash.

Subject free text comments will be listed after each NRS rating in listing 16.2.6.5 for all randomized subjects.

In addition to each NRS, subjects will be asked whether they would recommend the products to their family and friends who have gum problems at the end of the study. Responses (“yes” or “no”) will be summarized by the number and percentage of subjects in the ‘Test Toothpaste/Mouthwash’ treatment in Table 14.2.10.1.3.

#### **4.4.4 Handling of Missing Values/Censoring/Discontinuations**

For the primary analyses, missing data will not be replaced or imputed. Subjects who withdraw from the study prematurely will be included in the statistical analyses up to the point of discontinuation. Subjects who withdraw will not be replaced. In the event that a subject has no individual BI, MGI or TPI assessments available at a given visit, the Mean NBS, BI score, MGI score or TPI score will also be considered as missing for that visit.

MMRM analyses account for missing data using ‘a missing at random’ assumption, i.e., there is a systematic relationship between the propensity for missing values and the observed data, but not the missing data. Under such assumptions, MMRM is shown to provide unbiased estimates of the treatment effect whilst analysis of only complete cases using analysis of covariance (ANCOVA) is biased (Ashbeck, 2016; Baron, 2008).

Such complete case analysis requires a ‘missing completely at random’ assumption to remain unbiased and this is unlikely to hold, i.e., the fact that the data are missing is independent of the observed and unobserved data. Using an MMRM, it will therefore be assumed that a subject with missing data at one post- Baseline assessment visit would have obtained a similar efficacy result at that visit compared to a subject using the same investigational product with similar non-missing results at other timepoints (Baseline and the other post-Baseline assessment visits).

### **4.5 Analysis of Safety**

The safety profile of the study products will be assessed with respect to adverse events (AEs), incidents and OST/OHT abnormalities in this oral health study.

#### **4.5.1 Adverse Events and Serious Adverse Events**

All AEs will be reviewed by the Clinical Research Scientist or Designee prior to database lock and unblinding and will be coded to a system organ class (SOC) and preferred term (PT) using the Medical Dictionary for Regulatory Activities (MedDRA).

AEs will be classified as oral and non-oral on the AE page of eCRF.

Treatment emergent adverse events (TEAEs) are defined as new AEs that occur on or after the first study product use (if this date is missing, a suitable alternative will be used e.g. date of

randomization). AEs with an onset date/time prior to the first study product use at baseline visit will be considered as non-treatment emergent.

The following summary tables and listings will be presented by study product group.

- Table of TEAEs summary (Table 14.3.1.1)
- Table of TEAEs by SOC and PT (Table 14.3.1.2)
- Table of TEAEs by Oral/Non-Oral and PT (Table 14.3.1.3)
- Table of treatment related TEAEs by SOC and PT (Table 14.3.1.4)
- Table of treatment related TEAEs by Oral/Non-Oral and PT (Table 14.3.1.5)
- Listing of all AEs (Listing 16.2.7.1 for all randomized subjects; Listing 16.2.7.2 for non-randomized subjects)
- Listing of deaths (Listing 14.3.2.1)
- Listing of non-fatal SAEs (Listing 14.3.2.2)
- Listing of TEAEs leading to study or product withdrawal (Listing 14.3.2.3)
- Listing of TEAEs classified as Oral (Listing 14.3.2.4)

All incidents will be listed in Listing 16.2.7.3.

In the event that there is nothing to report, a null table or listing will be produced.

## **4.5.2 Other Safety Variables**

Other safety variables are listed below:

- OST examination
- OHT examination

### **4.5.2.1 OST Examination**

The OST examination will be accomplished by direct observation and palpation, using retraction aids as appropriate. The examination will cover the oral labial mucosa (including lips), buccal mucosa, mucogingival folds, gingival mucosa, hard palate, soft palate, tonsillar area, pharyngeal area, tongue, sublingual area, submandibular area and salivary glands. Any abnormal findings from the OST examination will be recorded in the eCRF with details of the abnormalities.

Where possible, this procedure should be conducted by a single clinical examiner.

OST will be summarized (number of subjects and percentages with abnormalities) by visit and study product in Table 14.3.4.1 for all subjects in the Safety Population. Abnormal findings from the OST examination will be listed (Listing 16.2.8.1) for all randomized subjects.

### **4.5.2.2 OHT Examination**

The OHT examination will be accomplished by direct observation, using retraction aids as appropriate. It will identify any grossly carious lesions, signs of erosive wear, enamel

Haleon Confidential

CCI

Statistical Analysis Plan Template v7.0

Page 33 of 44

irregularities, tooth fracture, gross generalized dental caries decay, decalcification and faulty restorations. Any conditions noted as 'Present' from the OHT examination will be described in the eCRF with details of the 'Present' condition.

The presence of any implants, fixed or removable dentures, fixed or removable orthodontic braces/bands, fixed orthodontic retainers, full crowns or veneers will be recorded. Where possible, this procedure should be conducted by a single clinical examiner.

Any conditions noted as 'Present' from the OHT examination will be listed (Listing 16.2.8.2) for all randomized subjects.

## **4.6 Analysis of Other Variables**

### **4.6.1 Repeatability of the Examiner**

Repeat MGI and TPI assessments will be performed by the clinical examiners at Visits 2, 3 and 4. At least 1 repeat assessment should be performed for each index on each clinical assessment day 'Repeat' subjects will be selected at random from those in attendance on any given assessment day. Different subjects should be used for repeat MGI and TPI assessments. Due to the invasive nature of the EBI assessment, it is not feasible to conduct an accurate repeatability assessment for this index.

There should be a delay of at least 10 minutes between the original and the repeat assessment for a given subject; ideally, repeat assessments should be separated by another subject. No other clinical procedure should be carried out on the selected subject between repeat assessments.

Scores from the first assessment must not be visible to the examiner/scribe when the repeat assessment is carried out.

The repeat MGI and TPI assessments will be compared to the respective original assessments (excluding any tooth surfaces assessed as missing or not qualified). The repeat assessments will not be used in any efficacy analysis.

The first and second assessments of each index will be analyzed with a Fleiss-Cohen weighted kappa coefficient ( $\kappa$ ), along with the 95% CI, to assess the intra-examiner reliability. Reliability will be deemed:

- Excellent if  $\kappa > 0.75$
- Fair to good if  $0.4 \leq \kappa \leq 0.75$
- Poor if  $\kappa < 0.4$

This analysis will be conducted on each respective index repeatability population (MGI population and TPI population).

#### 4.6.1.1 MGI Repeatability

The first and repeat values of the MGI for each tooth site will be combined and cross-tabulated for the MGI Repeatability population (Table 14.2.11.1). Only subjects with both first and repeat MGI assessments available for a given tooth site at the same visit will be presented and analyzed.

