8.3.4 Other Analysis(es)

Exploratory Analysis(es)

Toothpaste/Mouthwash Compared to Reference Toothpaste

The exploratory endpoints comparing the Toothpaste/Mouthwash (a toothpaste containing 0.454% w/w SnF₂ with a mouthwash containing 0.07% w/w CPC) to the SnF₂ Toothpaste (toothpaste containing 0.454% w/w SnF₂) will be analysed using the same MMRM model described above for the primary and secondary endpoints.

Exit Satisfaction Survey Questionnaire (toothpaste/mouthwash treatment arm)

A summary of the number and percentage of subjects reporting at each level of the NRS and the cumulative number of subjects reporting at each level or higher at Week 12 will be presented, and the numeric (integer) NRS score at Week 12 will be summarized descriptively, by the test product toothpaste and the test product mouthwash.

Property of Haleon- Confidential

May not be used, divulged, published or otherwise disclosed without the consent of Haleon

CCI

Abbreviated Clinical Protocol Template v1.0

Subject free text comments will be listed after each NRS rating.

In addition to each NRS, subjects will be asked whether they would recommend the products to their family and friends who have gum problems at the end of the study. Responses (“yes” or “no”) will be summarised by the number and percentage of subjects in the test product toothpaste and the test product mouthwash treatment respectively.

Repeatability of Examiner

The repeatability of the examiner in conducting the MGI and TPI assessments will also be performed for a random sample of subjects. The repeat assessments will be compared to the original assessments. The repeat assessments will not to be used in any efficacy analysis.

The first and second assessments of each index will be analyzed with a Fleiss-Cohen weighted kappa coefficient (κ), along with the 95% CI, to assess the intra-examiner reliability. Reliability will be deemed: Excellent if $\kappa > 0.75$, Fair to good if $0.4 \leq \kappa \leq 0.75$ and Poor if $\kappa < 0.4$. This analysis will be conducted on each respective index repeatability population (MGI population and TPI population).

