### 1.1 Study Design

This will be a single center, 12-week, randomized, controlled, examiner-blind, 3-treatment arm, parallel group, stratified by sex (male/female) study to evaluate the efficacy of using the

Toothpaste/Mouthwash twice daily in reducing gingivitis and plaque accumulation in a population with clinically measurable levels of gingivitis.

The clinical efficacy of the commercially available Toothpaste/Mouthwash will be compared with that of a commercially available, regular fluoride toothpaste with no known anti-gingivitis nor anti-plaque efficacy properties (Negative Control).

Study subjects will be healthy adult volunteers aged 18 and over with generalized clinically measurable plaque-induced gingivitis. Approximately 198 subjects (approximately 66 per group) will be randomized to ensure approximately 180 evaluable subjects (approximately 60 per group) complete the study (allow up to 10% dropout).

This study will consist of four study visits: Screening, Baseline, Week 6 and 12.

MGI, BI (NBS is derived from BI) and TPI will be used to assess gingival inflammation, bleeding and plaque accumulation. For MGI, instead of measuring 4 sites per eligible tooth, six sites per tooth (total up to 168 sites) will be assessed in order to evaluate gingival inflammation both Overall and Interproximal. EBI (Expanded BI) is an expanded version of the Angulated-bleeding index (AngBI) on the marginal gingiva, which measures all 6 sites surrounding a tooth and emphasizes the Interproximal area where most bleeding occurs.

At Screening visit (Visit 1), subjects will provide their written informed consent to participate in the study. Demographics, medical history, and current medications will be recorded, followed by an oral examination (oral soft tissue (OST), oral hard tissue (OHT) examination) and dentition exclusions, a gross gingival assessment and pocket depth assessment. Eligible subjects will be given a washout toothpaste and toothbrush to use in between the Screening and Baseline Visits.

Within 14-28 days of Screening (Visit 1), eligible subjects will return to the site for the Baseline visit (Visit 2) with overnight plaque (subjects will be instructed to abstain from oral hygiene for 12 hours [+6 hours; -2 hours] i.e., overnight immediately before the visit).

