The MGI assessment is a non-invasive evaluation which focuses on the visual symptoms of gingivitis (for example, redness, texture, edema). The MGI will be assessed on the buccal and lingual marginal gingiva and interdental papillae of all scorable teeth (second permanent molar to second permanent molar in each arch) by an appropriately qualified examiner. Three scores will be recorded buccally/labially (papilla and margin) and three scores lingually/palatally (papilla and margin). The scoring of the MGI will be performed under dental office conditions using a standard dental light for illuminating the oral cavity.

The MGI score has a range of 0 to 4.

The MGI scoring system is described in [Table 4-2](#).

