#### 4.6.1.2 TPI Repeatability

The first and repeat values of the TPI for each tooth site will be combined and cross-tabulated for the TPI Repeatability population (Table 14.2.11.2). Only subjects with both first and repeat TPI assessments available for a given tooth site at the same visit will be presented and analyzed.

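### The kappa confidence intervals for MGI and TPI make no allowance for up to 168 correlated tooth sites per subject, so the standard interval would overstate the precision of examiner reliability

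*SAP*

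**What the plan says.** For MGI and TPI, SAP 4.6.1 has the examiner repeat the scoring at Visits 2 to 4, with at least one repeat per index on each assessment day. On the analysis it says: "The first and second assessments of each index will be analyzed with a Fleiss-Cohen weighted kappa coefficient", "along with the 95% CI, to assess the intra-examiner reliability". Protocol 8.3.4 plans the same statistic.

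The unit of analysis is the tooth site. SAP 4.6.1.1 says "The first and repeat values of the MGI for each tooth site will be combined and cross-tabulated for the MGI Repeatability population", and SAP 4.6.1.2 says "The first and repeat values of the TPI for each tooth site will be combined and cross-tabulated for the TPI Repeatability population". Both require the two scores to come from the same visit. The repeatability populations in SAP 4.1.3 admit a subject with a repeat at any visit, so one subject may contribute more than one visit. Appendix 1 of the SAP lists one table per index (14.2.11.1 and 14.2.11.2) and mentions no split by visit.

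On the number of sites, SAP 1.1 says of MGI that "six sites per tooth (total up to 168 sites) will be assessed". TPI also has six scores per tooth (SAP 4.4.2.6).

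Neither document names a variance method for the interval, a per-subject kappa or any adjustment for clustering. The three reliability bands in SAP 4.6.1 are defined on kappa itself. The same section keeps repeat scores out of all efficacy analyses.

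**The concern.** The usual large-sample variance of a weighted kappa, computed from one cross-table, takes every pair as independent. Sites in one mouth are not. They share the subject's level of inflammation or plaque, and anything that alters the mouth between the two examinations moves many sites together. Protocol 5.3 to 5.5 make such a shift plausible: the listed order puts bleeding probing, plaque disclosure and TPI scoring between the first and the repeat MGI, although Protocol 6.2.5 says nothing else should be done in between. A programmer following SAP 4.6.1 as written has no instruction to adjust for this.

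At stake is how certain the examiner's reliability appears. One examiner makes all the gingivitis and plaque measurements (Protocol 6.1), and the bleeding index behind the primary endpoint cannot be repeated (SAP 4.6.1). The two kappas are therefore the only planned quantitative evidence from within the trial on that examiner's consistency, and the interval is their only stated measure of uncertainty.

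**Working it through.** **Cluster size.** SAP 4.4.2.4 scores "second permanent molar to second permanent molar in each arch", at most 28 teeth. 28 × 6 = 168, which reproduces the SAP's figure. The entry minimum of 20 teeth (Protocol 4.2) gives 20 × 6 = 120 if all are evaluable. The entry minimum of 40 evaluable surfaces serves as a lower bound.

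**Design-effect check.** Let m be the sites per subject and ρ the within-subject correlation of the site-level contributions to kappa. ρ is not in the documents; 0.005 to 0.20 is assumed.

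- Design effect: DE = 1 + (m − 1)ρ
- Correct width ÷ standard width = √DE
- Coverage of the standard 95% interval = 2Φ(1.96/√DE) − 1

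Example, m = 168 and ρ = 0.01: DE = 1 + 167 × 0.01 = 2.67; √2.67 = 1.63; coverage 77%.

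| m | Width ratio, ρ = 0.005 | ρ = 0.05 | ρ = 0.20 |
|---|---|---|---|
| 40 | 1.09 | 1.72 | 2.97 |
| 120 | 1.26 | 2.64 | 4.98 |
| 168 | 1.35 | 3.06 | 5.87 |

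**Simulation.** Five ordered categories (as MGI), quadratic weights, 156 sites per subject, 15, 30 or 60 repeat subjects, 500 runs per setting. Each site's latent score was a subject level plus a site deviation, with fresh measurement error at each examination. Some settings added a per-subject shift at the second examination. All of these values are assumed. Cells show true SD of kappa ÷ mean standard SE; coverage of the standard interval; coverage of a subject-level cluster-robust interval.

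| Raw-score ICC / shift SD | 15 subjects | 30 subjects | 60 subjects |
|---|---|---|---|
| 0.00 / 0 | 0.97; 95%; 93% | 0.96; 96%; 95% | 1.01; 95%; 95% |
| 0.12 / 0 | 1.33; 84%; 91% | 1.42; 84%; 93% | 1.35; 85%; 94% |
| 0.34 / 0 | 2.73; 54%; 88% | 2.62; 55%; 92% | 2.64; 54%; 94% |
| 0.34 / 0.2 | 2.82; 50%; 90% | 2.97; 52%; 91% | 2.91; 52%; 93% |
| 0.58 / 0.2 | 4.58; 30%; 88% | 4.56; 33%; 91% | 4.35; 37%; 92% |

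A separate simulation with 160 sites and 15 to 60 subjects, under its own assumptions, gave ratios of 1.3 to 4.1 and coverage of 38% to 90% whenever sites were correlated.

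**The two checks agree.** Inverting the design effect, ρ = (ratio² − 1)/(156 − 1). A ratio of 1.33 gives 0.769/155 = 0.005, and 4.58 gives 19.98/155 = 0.13. Both lie within the assumed range. The ρ that matters is much smaller than the raw-score ICC, but it is multiplied by a large m.

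**Absolute size.** In the clustered settings of the table, the standard half-width ran from 1.96 × 0.0036 = 0.007 to 1.96 × 0.0081 = 0.016. The true half-width ran from 1.96 × 0.0050 = 0.010 to 1.96 × 0.0370 = 0.073.

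**The case against.** The strongest reply is that the charge rests on silence. The SAP asks for a 95% interval without naming a formula, so a reader might infer that the plan prescribes independent pairs; it does not say so. That stands as a point of wording. It does not remove the problem, because nothing in either document would lead to any interval other than the standard one.

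A reader might also infer that the intervals are bound to be far too narrow. The documents cannot show that: they give no number of repeat subjects, no correlation and no expected kappa, and the shortfall ranges from slight to several-fold. Nor can one say in general that the effective sample is nearer the number of subjects than the number of sites. With 60 subjects and a ratio of 1.35, 9,360 pairs are worth about 9,360/1.82 = 5,140. With 15 subjects and a ratio of 4.58, 2,340 pairs are worth about 2,340/20.98 = 112.

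Third, little hangs on the interval. The bands use the estimate, repeat data enter no efficacy analysis, and the primary endpoint comes from an index with no repeat. Even the correct half-widths are small beside the Fair to good band, which is 0.75 − 0.40 = 0.35 wide. The position of the interval against a cut-off would change only if kappa fell within a few hundredths of it. All of this stands and limits the point to stated precision.

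**Conclusion.** The point holds in a limited form. The SAP pools tooth sites and asks for a 95% interval without allowing for within-subject correlation. The standard interval from that table would be too narrow under any positive within-mouth correlation, and zero correlation is not plausible for sites in one mouth. The simulated understatement was about 1.3 to 4 times, with coverage of roughly 40% to 90% and a little worse in the heaviest setting. These sizes rest on assumed correlations, shifts and 15 to 60 repeat subjects. They were simulated for a five-category index; TPI has six categories but the same site structure.

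A reader might go further and doubt the reliability classification or the efficacy results. The documents do not support that: the kappa estimate and its class do not depend on how the interval is computed, and no efficacy estimate, test or error rate uses the repeat data.

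**What to change.** Keep the Fleiss-Cohen weighted kappa and its bands. In SAP 4.6.1, specify for both MGI and TPI that the 95% interval comes from a bootstrap that resamples subjects, keeping all sites and visits of a subject together (for example 2,000 resamples with percentile limits). A subject-level cluster-robust variance would also do. Report the number of repeat subjects beside each kappa, and state whether the visits are combined in Tables 14.2.11.1 and 14.2.11.2.

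The cost is a short SAP addition, a little programming and a wider reported interval; no new data are needed. Coverage may still fall somewhat short of 95% if few subjects are repeated: the cluster-robust interval reached 88% to 91% in the clustered settings with 15 subjects and 92% to 94% with 60. The bootstrap was not simulated here.
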